Efficacy of Animal Assisted Therapy In the Treatment of Patients With Traumatic Brain Injuries

Principal Investigator:
[name]

Sponsor:
None

Site of Investigation: Inova Fairfax Hospital
Date of Protocol: June 1, 2014
Approved by IRB # 12-1216

ABSTRACT

Title: Efficacy of Animal Assisted Therapy in the Treatment of Patients with Traumatic Brain Injuries

Short Title: AAT in TBI

Rationale: The purpose of this study is to determine if patients who sustain traumatic brain injuries (TBI) and receive animal assisted therapy (AAT), using handler/dog teams registered to provide AAT, have improved functional outcomes in the intensive care units (ICU) and acute care hospital over those patients with TBI receiving no AAT.

Animal Assisted Care (AAC) is an ongoing and well-established program on the Inova Fairfax Hospital campus. AAT involves goal directed interactions with therapy dogs and their handlers designed to improve human physical, social, emotional and/or cognitive functioning.

Aims:

Aim 1: To determine if the use of animal assisted therapy in the plan of treatment of patients with TBI results in differences in scores on the Ranchos Los Amigos Scale, Glasgow Coma Scale, and in an increased ability to follow commands from those who do not receive AAT.

Aim 2: To determine if the use of animal assisted therapy in the plan of treatment of patients with TBI are discharged with a different degree of cognitive function than those who did not receive AAT.

Study Type: Prospective, experimental case-control study.

Study Design: The study population will include adult patients admitted to the trauma intensive care unit (TICU) of the Inova Fairfax Hospital with a TBI. Target enrollment will be 100 patients. Enrollment duration will be for 2 years from IRB approval.

Inclusion criteria:

- Patients aged 18-85 years admitted to TICU with severe TBI as identified by GCS ≤ 8 upon admission, or who progress within 96 hours of admission into a severe TBI as evidenced by a decrease in GCS to GCS < 8 .
- Those below GCS 5 will be considered for inclusion when they progress to GCS 5 or above.

Rationale: A GCS ≤ 8 meets the medical definition of a TBI. Experience of the Inova AAC Program and Trauma Team patients have demonstrated the best patient responses to AAT occurring when the patients have a GCS ≥ 5 .

Exclusion criteria:

Patients...

- who are intoxicated upon admission who experience resolution of neurological symptoms within 24 hours
- with a GCS ≤ 8 , who have no evidence of a TBI and have a blood alcohol level above the legal limit in the state of Virginia (0.8 or higher).
- with a known diagnosis of dementia prior to admission; patients who dislike or are allergic to dogs
- under isolation precautions with the exception of neutropenic precautions for any reason, including MRSA, C Diff, or VRE.
- unable to speak Spanish or English.
- those who would have religious/cultural reasons for avoidance of dogs
- patients who have a splenectomy

Study Methodology: Patients meeting study criteria will be enrolled in the study and randomized into either the intervention or control group. Those randomized into the intervention group will receive the animal-assisted therapy up to three times weekly, in addition to their usual care. Those randomized into the control group will receive standard of care.

Statistical Methods

Aim 1: The primary outcome for analysis will be the difference in Rancho Los Amigos Scale (RLAS) scores from pre-intervention to post-intervention (Δ RLAS). Weekly Δ RLAS will be compared between the AAT group and controls using nonparametric Wilcoxon rank sum tests (Mann-Whitney U tests). This analysis will be stratified by weeks 1-4 to determine whether the difference in Δ RLAS between AAT and controls changes over time.

Aim 2: The outcome for analysis will be the difference in Level of Commands (LOCmds) and Glasgow Coma Scale (GCS) and movement of extremities from pre-intervention to during-intervention and will be analyzed using the same methodology as in Aim 2.

1. INTRODUCTION

1.1 .Specific Aims

Aim 1: To determine if the use of animal assisted therapy in the plan of treatment of patients with TBI results in differences in scores on the Ranchos Los Amigos Scale, Glasgow Coma Scale, and in an increased ability to follow commands from those who do not receive AAT.

Aim 2: To determine if the use of animal assisted therapy in the plan of treatment of patients with TBI are discharged with a different degree of cognitive function than those who did not receive AAT.

1.2 .Hypothesis

Hypothesis 1 Patients sustaining TBI who participate in AAT will experience a faster and higher elevation in RLAS, GCS scales and the ability to follow commands than those TBI patients who do not receive AAT.

Hypothesis 2 Patients sustaining TBI who participate in AAT will experience a faster and higher elevation in cognitive function (as evidenced by the ability to follow multiple commands) than those TBI patients who do not receive AAT.

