1.3. Background and Significance

Patients who have sustained TBI can have significant decreases in their level of consciousness. This can interfere with the patients' abilities to (1) actively participate in their recovery and can inhibit their ability to breathe without artificial support, (2) obtain adequate nutritional input, and to (3) follow commands to increase range of motion and physical strength. Several of these patients have long intensive care unit and acute care lengths of stay.

The costs associated with the care of patients with TBI are quite high. In 1995, the total direct and indirect financial costs of patients with traumatic brain injuries were estimated at \$56 billion [1]. Schootman et al., estimate 254,500 TBIs required hospitalization in 1996 within the United States, with 5.4 billion US dollars charged to treat these injuries during acute hospitalization [2]. Patient age, increasing severity of injury and urban teaching hospitals were associated with higher charges. McGarry et al estimated the cost of hospitalization for moderate, serious, severe or critical TBI to be \$8,189, \$14,603, \$16,788 dollars, and \$33,537 respectively [3]. Costs also varied by injury type, averaging \$20,084 for gunshot wounds, \$20,522 for motor

vehicle crashes, \$15,860 dollars for falls, and \$19,949 for blows to the head. In this study we seek to demonstrate that the introduction of AAT can increase level of consciousness and cerebral function earlier and, therefore decrease cost of the provision of care to these patients.

Animal Assisted Care (AAC) is an ongoing and well-established program on the Inova Fairfax Medical campus. The main objective of the Animal Assisted Care Program is similar to the Pet Partner's[®] Program objective, which is to improve the patients' well-being through meeting some of their physical and emotional needs with the use of animals in the acute care environment^[4].

The AAC Program provides five modalities of therapeutic interventions (also known as animal assisted interventions (AAI):

1. **Animal Assisted Activities or Visitation**—the Pet Partner Team[®] Training Manual defines these as goal-directed activities designed to improve patients' quality of life through utilization of the human/animal bond. Animals and their handlers must be screened and trained. Activities may be therapeutic but are not guided by a credential therapist. ^[5]

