3.4. Endpoints/Outcome Measures

Patients enrolled in the study will participate until any of the following occurs:

1. choose to no longer participate
2. develop animal allergies
3. reach a RLAS of 7 or above
4. are discharged
5. are hospitalized for greater than or equal to 28 days.

3.5. Consent/Assent: Informed consent will be obtained by the PI or TICU RNs who are sub-investigators on the study. Patients or legally authorized representative of potential subjects will give consent. Patients who do not speak English or Spanish will not be consented.

3.6. Monitoring Subjects and Criteria for Withdrawal of Subjects from the Study.

Criteria for withdrawing subjects from the study are at patient and/or patient LAR request.

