4.2. Method of Data Analysis

Aim 1: To determine if the use of animal assisted therapy in the plan of treatment of patients with TBI results in higher scores on the Ranchos Los Amigos, Glasgow Coma Scale, an increased ability to follow commands, and an increased movement of extremities than those who do not receive AAT.

The difference in RLAS scores from pre-intervention to post the intervention will be the primary outcome for the analysis. The outcome, Δ RLAS, will be defined as RLAS during AAT/sham – RLAS pre-AAT/sham. Δ RLAS from each study visit (AAT or sham) will be averaged over each week of the study (weeks 1-4). To address the primary hypothesis, weekly Δ RLAS will be compared between the AAT group and controls using nonparametric Wilcoxon rank sum tests (Mann-Whitney U tests) in order to determine whether the AAT group has significantly higher Δ RLAS. This analysis will be stratified by weeks 1-4 to determine whether the difference in Δ RLAS between AAT and controls changes over time.

The difference in LOCmd scores and movement of extremities will be a secondary outcome of this study. Δ LOCmds and movement of extremities will be defined similarly to Δ RLAS, as the LOCmds and movement of extremities during AAT/sham – LOCmds and movement of extremities pre-AAT/sham, and the mean Δ LOCmds and movement of extremities will be calculated for each week of the intervention (1-4). Weekly

Δ LOCmd scores and movement of extremities will be compared between study groups (AAT vs. controls) using nonparametric Wilcoxon rank sum tests. This analysis will be stratified by weeks 1-4 to determine whether the difference in Δ LOCmd and movement of extremities between AAT and controls changes over time.

GCS scores are routinely collected every hour by the TICU nursing staff. Medical charts will be reviewed to record the GCS scores during the hour immediately before and immediately after the intervention (or sham) is implemented. Δ GCS will be defined as GCS after AAT/sham – GCS pre-AAT/sham. Weekly Δ GCS scores will be compared between study groups (AAT vs. controls) using nonparametric Wilcoxon rank sum tests. This analysis will be stratified by weeks 1-4 to determine whether the difference in Δ GCS between AAT and controls changes over time.

Aim 2: To determine if the use of animal assisted therapy in the plan of treatment of patients with TBI are discharged with a higher degree of cognitive function than those who did not receive AAT.

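### Both hypotheses claim faster recovery, but every planned comparison is a within-session score change, so speed of recovery is not tested

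*Protocol*

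**What the plan says.** Protocol section 1.2 makes two claims about speed. Under Hypothesis 1, AAT patients "will experience a faster and higher elevation in RLAS, GCS scales and the ability to follow commands" than patients without AAT. Under Hypothesis 2 they "will experience a faster and higher elevation in cognitive function (as evidenced by the ability to follow multiple commands"). Section 1.3 repeats the idea and rests its cost argument on it: the study seeks to show that "the introduction of AAT can increase level of consciousness and cerebral function earlier".

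Section 4.2 fixes the analysis. The primary outcome, ΔRLAS, "will be defined as RLAS during AAT/sham – RLAS pre-AAT/sham". ΔRLAS "from each study visit (AAT or sham) will be averaged over each week of the study (weeks 1-4"), and the weekly values are "compared between the AAT group and controls using nonparametric Wilcoxon rank sum tests (Mann-Whitney U tests"). Section 4.2 names this as the test of the primary hypothesis, under Aim 1 and again under Aim 2. Command level, movement of extremities and the Glasgow Coma Scale (GCS) are handled in the same way, with GCS taken from the hour before and the hour after the session. The abstract describes the same approach.

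Section 3.4 is headed as endpoints and outcome measures, but it lists only the events that end participation. One of them is to "reach a RLAS of 7 or above". The Intervention Group and Control Group parts of section 3 also use RLAS 7 only to stop data collection.

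**The concern.** *Faster* is a statement about how soon a patient gets better. A difference between two scores taken around one session does not measure that. Splitting the tests by week does not change this: section 4.2 gives the purpose of the split as seeing whether the between-arm difference in session change alters over the four weeks.

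Two errors of interpretation follow. If AAT shortens recovery through gains that appear between sessions, the planned tests have no means of showing it. If AAT produces a brief lift in score during the visit and nothing lasting, the planned tests may be positive, and section 1.2 invites that result to be reported as faster recovery. The exit at RLAS 7 adds to the problem. Patients who recover soonest stop contributing to later weeks, and their speed is credited nowhere.

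**Working it through.** **1. What the outcome contains.** Let L be the RLAS level just before a session and r the response during it. Then Δ = (L + r) − L = r, and L cancels. Over a stay,

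total change = sum of within-session changes + sum of between-session changes.

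Only the first sum enters the analysis, as weekly means. Suppose patient A goes from RLAS 3 to 7 in ten days, with every gain between sessions, and patient B stays at 3 for 28 days. Both have Δ = 0 at every session, and the planned test cannot tell them apart. This step needs no assumption beyond the definition in section 4.2.

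**2. Search for any other comparison of speed.** The comparisons in the abstract and section 4.2 cover RLAS, command level, movement of extremities and GCS. All are during or after minus before. None is a time to a level, a slope across sessions or a length of stay.

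**3. Illustration by simulation.** There were 50 patients per arm (section 4.1) and 2,000 simulated trials. The rest is assumed: starting RLAS of 2, 3 or 4 with equal probability; 12 sessions over 28 days; exit at RLAS 7; two-sided 5% level. After each session the level rises by one step with a given probability. The in-session change is 0 or 1, is transient and has its own probability. The time comparison is a rank test on time to RLAS 7, set to 28 days if not reached.

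| Setting | Step probability, AAT vs control | Session-response probability, AAT vs control | RLAS 7 by day 28, AAT vs control | Weekly tests reject (weeks 1, 2, 3, 4) | Time test rejects |
|---|---|---|---|---|---|
| Faster, same session response | 0.40 vs 0.25 | 0.15 vs 0.15 | 75% vs 37% | 4.3%, 4.8%, 4.4%, 5.0% | 97% |
| Same speed, larger session response | 0.25 vs 0.25 | 0.30 vs 0.15 | 37% vs 37% | 87%, 85%, 81%, 73% | 4.7% |

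In the first setting the weekly tests reject at about the false-positive rate, and about 24 AAT and 40 control patients remain in week 4. In the second setting the weekly tests are usually positive with no difference in speed.

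**4. What a time-to-RLAS-7 comparison could detect.** The Protocol gives no alpha, power or event rate, so there is no stated power to reproduce. Using Schoenfeld's approximation for a log-rank test with 1:1 allocation (section 3.3), N = 100 (section 2.4) and an assumed two-sided 0.05:

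power = Φ(√(events × 0.25) × ln HR − 1.96).

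For 50 events and HR 2.0: √12.5 × 0.693 = 2.45; 2.45 − 1.96 = 0.49; power 69%.

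| Patients reaching RLAS 7 (assumed) | Power, HR 1.5 | Power, HR 2.0 | HR detectable at 80% power |
|---|---|---|---|
| 30 | 20% | 48% | 2.78 |
| 50 | 30% | 69% | 2.21 |
| 70 | 40% | 83% | 1.95 |
| 90 | 49% | 91% | 1.81 |

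Events needed for 80% power: 191 at HR 1.5, 101 at HR 1.75 and 66 at HR 2.0.

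**The case against.** *The simulated result is built in.* The first setting places the whole gain in speed between sessions. If AAT also produced in-session gains that persisted, Δ would pick up part of the recovery. This stands as a limit on the simulation: faster recovery need not always leave the weekly tests negative. It does not rescue the tests as measures of speed, because step 1 holds whatever the mechanism.

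*Faster elevation need not mean time to a milestone.* It could mean a steeper course over the stay. That is fair, but no slope across sessions is planned either.

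*A statistical analysis plan may supply the missing analysis.* None is at hand, and one could add it. But the Protocol itself names the weekly ΔRLAS comparison as the test of the primary hypothesis, so hypothesis and test already disagree within this document.

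*A reader might infer that the trial cannot test speed.* The documents do not support that. RLAS and command level are scored serially in both arms, up to three times weekly, and RLAS 7 ends participation in both. Speed is untested by the planned analyses, not untestable.

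*A reader might also take the 97% in the simulation as the power of the remedy.* It is not. Reaching 75% versus 37% by day 28 implies an average hazard ratio of about ln(0.25)/ln(0.63) = 3.0. The simulation has no deaths and no earlier discharges, and it gives every patient a full 28 days from entry. No section of the Protocol supports those inputs.

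**Conclusion.** The mismatch is real and lies in the Protocol: section 1.2 claims faster recovery, and no comparison in the abstract or section 4.2 measures it. This follows from the definition of Δ alone. The simulated rejection rates show the size of the problem under assumed inputs and are not forecasts for this trial.

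Nor should a reader infer that the *higher* part of each hypothesis is properly tested. A within-session change does not measure the level reached over the stay either, and the remedy below deals with speed only.

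The trial remains analysable, but a central claim has no test and a positive result could be misread as supporting it. The point should be corrected before analysis. An added time comparison would address the claim, probably with modest power: a hazard ratio of 1.5 would be missed more often than not across the assumed range of 30 to 90 events.

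**What to change.** Add one paragraph to section 4.2, as the stated test of *faster*, comparing the arms by randomised group on:

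- days from randomisation to the first recorded RLAS of 7 or above at any scheduled scoring, before or after a session (Hypothesis 1);
- days from randomisation to the first recorded command level of 2-step or more (Hypothesis 2).

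Use cumulative incidence with Gray's test, with death and earlier discharge as competing events and censoring at hospital day 28. State that the weekly Δ tests do not address speed.

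The RLAS milestone should be the same event that ends participation. If only pre-session scores counted, a patient who first scored 7 after a session would leave without an event. Should AAT lift scores in session, those losses would fall mainly in the AAT arm. The paragraph also needs a rule for a patient who leaves at RLAS 7 with no 2-step command recorded.

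If this analysis is not wanted, delete *faster* from both hypotheses.

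**Cost.** The analysis is small and needs no new visit, score or change in care. It does assume that each scoring and exit is dated; the data collection sheet is not shown, so this should be confirmed. Milestone dates are known only to within the gap between scoring visits, each hypothesis gains one secondary test, and power is likely to be modest.

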3. STUDY METHODS AND PROCEDURES

All patients admitted to the TICU will have a documented GCS in the medical chart as a part of clinical care. [name] (LH), the study PI, and the Trauma Intensive Care Unit RN subinvestigators will screen the TICU census daily for new patients to identify those admitted with GCS ≤ 8 that meet study criteria. Eligible patients will be followed by the PI or the TICU RNs until the patient is assessed at GCS of 5 or above.

1. Patients with a GCS of 5 or above will be screened for eligibility. Those eligible will be invited to participate and consent will be obtained by study personnel.
2. Consenting subjects will be randomized to the intervention or control arm of the study

3. For patients randomized to the intervention arm, study personnel (PI or TICU RNs) will request a doctor's referral. A referral will be made to LH who will arrange for the patient to receive the intervention with the dog.
4. The control group will be receiving standard of care bedside interventions. During the control measurement period, the only person present will be the bedside nurse who records the measurements.
5. Study personnel will record the RLAS, GCS, Level of Commands, and Movement of Extremities within 24 hours of obtaining consent and order.

Intervention Group

1. When the patient is randomized to the treatment arm, the PI will refer the case to one of the AAC handler/dog teams approved for work on the study for the intervention. The AAC handler will respond within 3 days and will request data measurements be taken by the bedside RN. These measurements will include (see attachments for data collection sheet):
 - A. RLAS Score
 - B. GCS Score
 - C. Level of Command (LOCmd)-0, 1 or 2 or 3-step
 - D. Movement of Extremities
2. Following the recording of the above measurements, the AAC team will provide AAT to the patient.
3. Immediately following the intervention, the same scores will be measured by the same licensed healthcare professional.

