To address the primary hypothesis, weekly Δ RLAS will be compared between the AAT group and controls using nonparametric Wilcoxon rank sum tests (Mann-Whitney U tests) in order to determine whether the AAT group has significantly higher Δ RLAS. This analysis will be stratified by weeks 1-4 to determine whether the difference in Δ RLAS between AAT and controls changes over time.

The difference in LOCmd scores will be a secondary outcome of this study. Δ LOCmd and movement in extremities will be defined similarly to Δ RLAS, as the LOCmds and movement of extremities during AAT/sham – LOCmds and movement of extremities pre-AAT/sham, and the mean Δ LOCmds and movement of extremities will be calculated for each week of the intervention (1-4). Weekly Δ LOCmd scores and movement of extremities will be compared between study groups (AAT vs. controls) using nonparametric Wilcoxon rank sum tests. This analysis will be stratified by weeks 1-4 to determine whether the difference in Δ LOCmds and movement of extremities between AAT and controls changes over time.

4.3. Data Storage: The data will be stored on a password protected computer in the AAC office for three years in a Microsoft Excel 2010 database and then destroyed. Only study personnel will have access to these data.

4.3.1. Data Management: Information about study subjects will be kept confidential and managed according to the requirements of the Health Insurance Portability and Accountability Act of 1996 (HIPAA). Privacy and confidentiality of all enrolled patients will be maintained. All data collection tools will be taken to the AAC Office and will be entered by LH into the secure study data base. Consent documents and the regulatory binder will be kept in the Trauma Research Manager's office. The Trauma Department suite is locked, and the Trauma Research Manager's office is locked.

4.3.2. Records Retention: The data will be stored for three years in a Microsoft Excel 2010 database and then destroyed.

5. HUMAN SUBJECTS PROTECTION (RISKS, BENEFITS, and ALTERNATIVES)

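### Hypothesis 2 is about following multiple commands and Aim 2 about function at discharge, but the Aim 2 LOCmd analysis repeats Aim 1's weekly mean change, which single-command gains alone can drive

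*Protocol*

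**What the plan says.** Section 1.2 of the protocol gives two hypotheses that involve commands. Hypothesis 1 covers RLAS, GCS and "the ability to follow commands than those TBI patients who do not receive AAT". Hypothesis 2 predicts a faster and higher elevation in "cognitive function (as evidenced by the ability to follow multiple commands"). As far as commands go, the word for more than one is what separates the two. Aim 2, in the abstract and in sections 1.1 and 4.2, asks about cognitive function when patients are discharged.

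The only command measure collected is "Level of Command (LOCmd)-0, 1 or 2 or 3-step" (section 3, same items in both arms).

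Under Aim 2, section 4.2 puts ΔRLAS first and then says "The difference in LOCmd scores will be a secondary outcome of this study". The change is "LOCmds and movement of extremities during AAT/sham – LOCmds and movement of extremities pre-AAT/sham"; next, "the mean Δ LOCmds and movement of extremities will be calculated for each week of the intervention (1-4"); and finally "Weekly Δ LOCmd scores and movement of extremities will be compared between study groups (AAT vs. controls) using nonparametric Wilcoxon rank sum tests". The LOCmd paragraph under Aim 1 gives the same definition, averaging and test.

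The abstract's statistical methods describe Aim 2 more widely: "The outcome for analysis will be the difference in Level of Commands (LOCmds) and Glasgow Coma Scale (GCS) and movement of extremities".

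**The concern.** The protocol fixes the outcome, its formula, the averaging and the test for Aim 2, and that outcome does not measure what Hypothesis 2 describes. A difference on the 0 to 3 scale records how many levels a patient moved during a session. It does not record whether the patient ended the session following more than one command, and a weekly average of within-session changes says nothing about the level at discharge. No comparison in section 4.2 looks at the multi-step levels or at the level reached. The GCS and limb movement that the abstract adds do not measure multiple-command following either.

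Entry requires a GCS of 8 or below, with a floor of 5, so many patients may well start with no command-following, and the early gains would then be mostly from 0 to 1. That gain already belongs to Hypothesis 1. What is at stake is a conclusion about higher cognitive function, which section 5.2 treats as potentially important for the standing of the therapy, drawn from data in which nobody needs to have followed multiple commands.

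**Working it through.** There is no plan figure to reproduce. The protocol states no alpha, power, effect size or start distribution for LOCmd. The inputs taken from it are about 50 patients per arm (sections 2.4 and 4.1), 1:1 allocation (3.3), up to three sessions a week (section 3), the 0 to 3 scale, the during-minus-pre change, and the rank sum test. A two-sided 5% level is assumed, and multiple commands is read as 2 or 3 steps, the only levels on the scale with more than one.

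**Step 1, scoring.** Change = during − pre. The moves 0→1, 1→2 and 2→3 each give +1. The move 0→2 gives +2 and 0→3 gives +3. So a gain that stays below multi-step following scores the same as a one-level gain into or within that range, but less than a larger jump.

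**Step 2, how few single-command gains suffice.** Suppose each patient's weekly mean change is 0 or 1, with kA gainers of 50 on AAT and kC of 50 among controls. Let p = (kA + kC)/100. The tie-corrected rank sum statistic is then

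z = (kA/50 − kC/50) / √[p(1 − p)(2/50)] × √(99/100).

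For kA = 4 and kC = 0: p = 0.04, the root is √(0.04 × 0.96 × 0.04) = 0.0392, and z = 0.08/0.0392 × 0.995 = 2.03, so p-value = 0.042. If every AAT gain is 0→1 and no control gains:

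| AAT patients moving 0→1 | Rank sum p (asymptotic) | Exact p |
|---|---|---|
| 3 | 0.080 | 0.242 |
| 4 | 0.042 | 0.118 |
| 5 | 0.023 | 0.056 |
| 6 | 0.012 | 0.027 |

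Between 4 and 6 patients of 50 are enough, with nobody above one step. On an outcome of 2 steps or more, every row is 0/50 against 0/50.

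**Step 3, a case that points the wrong way.** Let 15 AAT patients move 0→1 and 5 controls move 1→2. Then p = 0.20, the root is √(0.20 × 0.80 × 0.04) = 0.08, and z = 0.20/0.08 × 0.995 = 2.49, so p-value = 0.013 in favour of AAT. The only multi-step followers are controls: 0/50 against 5/50, Fisher p = 0.056, pointing toward control.

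**Step 4, how often (illustrative).** One week was simulated with 50 per arm, three sessions and each patient's start level held fixed across them. Patients start at level 0 or 1. The control 0→1 gain is 5% per session and the 1→2 gain is 5% in both arms, so AAT has no effect on multi-step following. The table gives the share of trials in which the planned test is significant, for four AAT 0→1 gain rates per session:

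| Start at level 0 | 10% | 15% | 20% | 25% |
|---|---|---|---|---|
| 80% | 25% | 66% | 90% | 98% |
| 50% | 15% | 33% | 57% | 77% |
| 20% | 5% | 9% | 15% | 21% |

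A repeat run agreed within about 2 percentage points. In the 80% setting, the comparison of patients reaching 2 steps or more was significant in under 1% of trials (Fisher's test is conservative here). With equal 5% gains in both arms the rank sum test rejected in about 4.5%, so the test itself is sound. The single-command effect is what it detects.

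**The case against.** The strongest reply is that Hypothesis 2 speaks of an elevation, that a change score on a stepped command scale is a natural measure of elevation, and that the parenthesis may simply name that scale. The protocol gives no cut-point for multiple commands. This stands in part: 2 steps or more is a reading of the text, not a stated threshold. On the looser reading, though, the command part of Hypothesis 2 adds nothing to Hypothesis 1, and the wording still needs repair.

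A reader might infer that the plan would declare Hypothesis 2 proven whenever ΔLOCmd is significant. The document does not support that. It states no alpha and no rule tying ΔLOCmd to Hypothesis 2, and it labels LOCmd secondary, after ΔRLAS. The narrower statement is that such a result would not support the hypothesis as worded, and LOCmd is the only measure collected that could bear on it.

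A reader might also infer that a 0→1 gain always counts as much as any multi-step gain. It does not: 0→2 scores +2. The equality holds for one-level moves. Ranks also treat +1 and +2 alike when they are set against controls with no gain, but not in general.

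The simulated rates follow from their assumptions. An effect confined to 0→1 was put in, and the results fall sharply as fewer patients start at 0, which is likely in later weeks because follow-up can run to 28 days. They show that the problem can be large, not that it will be.

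Finally, a responder definition is often left to a statistical analysis plan. Here the protocol itself already fixes the Aim 2 outcome and test, so the mismatch lies in this document.

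**Conclusion.** The point holds as a mismatch between a stated hypothesis and the analysis fixed for it. The Aim 2 LOCmd analysis duplicates Aim 1's, gives 0→1 full credit, and addresses neither multi-step following nor status at discharge. The scoring fact needs no assumption. That 4 to 6 single-command gains in 50 can reach significance assumes no control gains and a two-sided 5% level. The frequency cannot be estimated from the protocol: in the settings tried it ran from about 5% to 98%. The primary outcome, ΔRLAS, is not touched. This should be corrected because one of the two hypotheses is not tested as written, but it concerns a secondary outcome and does not undermine the trial.

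**What to change.** In section 4.2 and the abstract, replace the duplicated Aim 2 LOCmd analysis with a between-arm comparison of the proportion of patients at LOCmd 2 steps or more at the last recorded assessment before discharge or study exit. Account for LOCmd at the first, pre-intervention assessment, for example by stratifying on it or including it in a logistic model. Say which reading of the last session counts, the same in both arms, and how deaths are handled. Keep weekly mean ΔLOCmd, ΔGCS and movement of extremities under Aim 1.

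Counting patients who ever reach 2 steps would not do. It includes those already there at the start, depends on the number of sessions, and does not answer the discharge question.

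If the sponsor prefers to keep only ΔLOCmd, reword Hypothesis 2 so that it claims a change in command level and not multiple-command following.

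The cost is wording only, since LOCmd is already recorded at each session. The threshold outcome is less sensitive than the mean change, and last assessments fall at different times because patients leave at discharge, at RLAS 7 or at 28 days. The mean change remains available under Aim 1.
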